Retrograde analysis of data of all patients presented to Aboul Reesh uveitis clinic taking biologics from January 2017- January 2020. In our hospital, the rationale for using biologics was a high frequency of sight-threatening, frequent recurrences of uveitis or intolerance to steroids or other immunosuppressive drugs, with severe adverse reactions.

Sample size:

It is expected to review 250 patients files of Aboul Reesh uveitis clinic to find all JIA patients with ocular inflammation treated with biologics.

Inclusion criteria

1. Both genders
2. Age up to 16 years
3. Diagnosed JIA according to rheumatological criteria with ocular affection
 - Any type of arthritis (oligoarticular, polyarticular, systemic onset, ocular JIA)
 - ANA positive or negative
4. Uncontrolled uveitis or frequent relapses

Exclusion criteria:

1. Patients without definitive diagnosis as JIA

2. JIA patients on biologics without ocular affection (for systemic control) or with uveitis controlled without the use of biologics
4. Patients without adequate duration for follow-up (less than 3 months) or lost follow up data
5. Patients without available data prior to the start biologics (to compare control of the uveitis)

Methodology

Data will be obtained from by retrospective analysis of all files of patients with JIA from the Abou El Reesh ophthalmology outpatient clinic.

The patients with ocular inflammation treated by biologics will be further analyzed.

The data analyzed will divided into pre and post biologic treatment:

In both we will document-

-Baseline BCVA (in logMar notation)

- Grading of ocular inflammation

(Anterior chamber and vitreous cells were graded as +0.5, +1, +2, +3 and +4 according to the guidelines of the Standardization of Uveitis Nomenclature Working Group)

- Number of relapses in one year

- Development of sight threatening complication

- Dose and frequency of systemic, regional and topical steroids

- Other interventions required

Treatment parameters to be analyzed include type, duration and dose of biologic agent used, time taken to reach inflammation control, adverse effects, and time taken to develop those adverse effects.

Improvement or worsening of activity of inflammation was assessed according to the Standardization of Uveitis Nomenclature Group's directions (2 step improvement or worsening of cells/flare)

Treatment was determined as efficacious if one of the following was fulfilled:

1. No relapses or decrease in the number of relapses

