2. Decrease in dose of topical or systemic steroids
3. Improvement of BCVA of at least two lines

Statistical analysis plan:

All data will be entered into Excel spreadsheets (Microsoft Corporation, Redmond, WA, USA). All statistical analyses will be performed using IBM SPSS version 22.0 software (IBM Corp., Armonk, NY, USA). Descriptive statistics will be summarized as the mean \pm standard deviation for numerical data, frequencies and percentages for categorical data. The ANOVA -test and Pearson moment correlation will be used to compare the means for the numerical data and to identify correlations between them. Chi-square test will be used to compare categorical data. P-values ≤ 0.05 will be considered statistically significant.

References

- 2) Qian Y, and Nisha R. (2010) Juvenile Idiopathic Arthritis Associated Uveitis. *Curr Opin Ophthalmol.* 21(6): 468–472. doi:10.1097/ICU.0b013e32833eab83

Retrospective Analysis of the Use of Biologics for Juvenile Idiopathic Arthritis Related Uveitis in Abou El Reesh Pediatric Hospital, Cairo University

First version, 1st march 2020

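### One unadjusted 0.05 threshold covers every test, with no primary outcome and nothing labelled exploratory, so the plan does not limit chance findings

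*Combined protocol and SAP*

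**What the plan says.** The Statistical analysis plan gives three kinds of test and one threshold:

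- For numerical data: "The ANOVA -test and Pearson moment correlation will be used to compare the means for the numerical data and to identify correlations between them".
- For categorical data: "Chi-square test will be used to compare categorical data".
- For all of them: "P-values ≤ 0.05 will be considered statistically significant".

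The variables, pairs and number of tests are not listed.

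The Methodology section supplies the material to be tested: "The data analyzed will divided into pre and post biologic treatment". Six items are recorded in both periods. They are visual acuity, inflammation grade (anterior chamber and vitreous cells), relapses over a year, sight-threatening complications, steroid use (dose and frequency for three routes) and other interventions. Treatment parameters are added: type, duration and dose of the biologic, time to control, adverse effects and time to adverse effects.

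The same section calls treatment efficacious when any one of three criteria is met: no relapses or fewer of them, a lower steroid dose, or better visual acuity. This definition is not called primary, and no test is tied to it.

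The Sample size section gives 250 files to be reviewed. It does not give the number of patients to be analysed, a power or an effect size.

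**The concern.** The threshold is a stated rule, so this is more than a missing detail. Followed as written, it gives the same standing to any outcome or correlation that reaches 0.05. Nothing in the document tells a reader which result was the planned test and which was the best of many. The Background section sets out several aims (controlling inflammation, preventing complications, weighing benefit against side effects) without ranking them, so the aims do not settle it either.

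The phrase "to identify correlations between them" adds an open-ended set of further tests under the same threshold. In a retrospective review, where all the outcomes already sit in the files, naming the main outcome beforehand is the chief protection against choosing it afterwards.

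**Working it through.** The plan states no family-wise error rate, power or number of tests, so there is no figure of its own to reproduce. The only stated input is the per-test threshold of 0.05. The test counts below are assumptions built from the Methodology list.

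**Counting the pre/post comparisons.** One test per item gives 6. Splitting the items gives acuity 1 + cell grades 2 + relapses 1 + complications 1 + steroids 6 (dose and frequency × 3 routes) + other interventions 1 = 12.

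**Independent tests, all nulls true.** The chance of at least one false positive among *m* tests is 1 − 0.95^m.

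| m | Calculation | Chance |
|---|---|---|
| 6 | 1 − 0.7351 | 26.5% |
| 12 | 1 − 0.5404 | 46.0% |
| 13 | 1 − 0.5133 | 48.7% |
| 14 | 1 − 0.4877 | 51.2% |

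So 50% is passed at 14 tests. Six comparisons would need 8 correlations to get there, and twelve would need 2.

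**Positive dependence.** Outcomes in the same child are likely to be related. In a simulation of two-sided tests whose statistics share a common correlation, the figures fall:

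| m | 0.3 | 0.5 | 0.7 |
|---|---|---|---|
| 6 | 24.1% | 20.8% | 16.5% |
| 12 | 39.6% | 31.9% | 23.1% |
| 14 | 43.8% | 34.7% | 25.0% |

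**Unpaired tests on paired data.** The plan does not say that the pre/post tests are paired. An unpaired comparison of two means from the same patients, with within-patient correlation ρ, has actual size 2 × [1 − Φ(1.96/√(1 − ρ))].

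- ρ = 0.3: 1.96/0.837 = 2.34, size 1.9%. Six independent tests give 11%.
- ρ = 0.5: 1.96/0.707 = 2.77, size 0.6%. Six independent tests give 3%.

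**Adding correlations.** Not every pair is a true null when the drug has no effect: inflammation grade may well be related to acuity or steroid dose in any case. A stricter count takes only the pre/post changes plus biologic dose and duration against each outcome. That is 6 + 2 × 6 = 18 tests, or 12 + 2 × 12 = 36. A simulation with an assumed 40 patients, null change scores and paired tests gives:

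| Correlation between outcomes | 18 tests | 36 tests |
|---|---|---|
| 0 | 61% | 84% |
| 0.3 | 57% | 79% |
| 0.5 | 51% | 68% |
| 0.7 | 42% | 55% |

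**The case against.** The strongest reply is that this is a single-centre file review meant to describe how biologics were used, and that it already has a deciding criterion, the three-part efficacy rule, which does not depend on a P-value. Part of this stands. The efficacy rule is the nearest thing to a main outcome, and a descriptive study need not ban all secondary testing. But the rule classifies individual patients and is not linked to any comparison. The plan also goes beyond description when it sets a significance threshold.

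A second reply is that the error may be modest. This also stands in part: for the pre/post tests alone the chance stays below one half, and unpaired testing would bring it well down. That protection would come from a mis-specified test, at a cost in power, and it would not extend to the Pearson correlations.

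A reader might infer that at least one false claim is likely even if biologics do nothing. The documents do not support that. They give no test count, and the chance passes 50% only once enough correlations are added, and then not under every degree of dependence.

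A reader might also infer that every pair of numerical variables will be tested. The plan says only that correlations will be sought, without saying which. Counting all pairs as nulls would also overstate the error, because correlations that are truly non-zero are not false findings.

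**Conclusion.** The concern holds in a limited form. One 0.05 threshold governs at least six pre/post items and an unlisted set of correlations, with no primary outcome, ordering, adjustment or exploratory label. The error rate over the whole set of tests is therefore uncontrolled, and the planned test cannot be told apart from the others.

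Its size can only be given as a range: 26% to 46% for 6 to 12 independent null comparisons, about 21% to 32% if the test statistics correlate at 0.5, and above 50% from 14 independent nulls. These figures rest on assumed counts, true nulls and properly sized tests.

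Multiplicity is also not the only route to a misleading result. The Inclusion criteria select children whose uveitis is uncontrolled or relapses often, and there is no control group. A fall after treatment, above all in "Number of relapses in one year", can reflect regression to the mean. That is bias, and no choice of threshold removes it.

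**What to change.** Before any file is opened, add a short paragraph to the Statistical analysis plan that:

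1. names one primary outcome and one paired pre/post test of it at 0.05;
2. reports all other outcomes as estimates with 95% intervals, labelled exploratory;
3. replaces the open search for correlations with a short named list, also labelled exploratory;
4. says whether the efficacy rule is the primary outcome or a descriptive summary;
5. states that these steps control chance findings only, and that a pre/post improvement in selected patients without a control group is not proof of a drug effect. If relapses are chosen as primary, this caution applies with most force.

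If the investigators want to keep formal tests for other outcomes, they could list and adjust them instead. Bonferroni would put the threshold at 0.05/6 = 0.0083 for six tests or 0.05/12 = 0.0042 for twelve.

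No new data are needed. The cost is that fewer results can be called significant.
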